We will follow the patients via office visit at four and eight weeks after initiation of therapy. Measurements of the granulation tissue and photographs will be obtained pre treatment and at each post treatment visit. In addition parents will be asked to fill out a pre and post treatment survey regarding improvement in symptoms. We plan to enroll 120 patients total with the intention of having 40 participants in each group.

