4.0 Selection of Patients

- **4.1** *Inclusion Criteria (list):* birth 17 years of age, granulation tissue present around gastrostomy tube site for at least 1 week
- **4.2** Exclusion Criteria (list): allergy to any of the potential medications (silver nitrate or kenalog), Non-english speaking patients will be excluded due to inability to effectively communicate study details, risks and benefits.
- 4.3 Age Range: 0-17 years of age

5.0 Study Methodology:

Prospective, randomized study utilizing children ages birth to 17 years, with granulation tissue present around their gastrostomy tube for at least one week. Patients will be randomized to one of the three treatment groups in equal numbers. Once the inclusion criteria are met, informed consent will be obtained from the parent and randomization will occur. Patients will be randomized to either Kenalog (0.5% ointment three times a day for three weeks) or cauterization with silver nitrate (three times a week for three weeks) or abrasion/washing with a soap washcloth (once daily for three weeks). At the end of the three week period, if granulation tissue is still present, the patients will undergo a rest period of one week, followed by another three week course. These children will be followed at four weeks and eight weeks via clinic visits. At the clinic visits, photographs and measurements will be obtained and parent surveys completed.

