10.0 Statistical Considerations

ANOVA and Chi square tests will be used to evaluate the differences between the three treatment groups. Actual measurements of the granulation site, blinded evaluation of the pictures and analysis of pre and post surveys will be incorporated into the data analysis.

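### Section 10.0 assigns no test to the picture and survey outcomes and names only chi-square for categories; if these are ordered grades, chi-square would ignore the order and could cost power.

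*Combined protocol and SAP*

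**What the plan says.** The statistical plan is two sentences long. The first reads: "ANOVA and Chi square tests will be used to evaluate the differences between the three treatment groups". The second lists what will be analysed. It starts with the site measurements and goes on: "blinded evaluation of the pictures and analysis of pre and post surveys will be incorporated into the data analysis". Neither sentence links a test to an outcome.

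The survey is described in Sections 1.0 and 3.0: "parents will be asked to fill out a pre and post treatment survey regarding improvement in symptoms". No response format is given for it, and no grading scheme for the photographs. No rank or ordinal method appears anywhere, and no use of the pre-treatment survey answer in the analysis is described.

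The planned size is stated without a power calculation: "We plan to enroll 120 patients total with the intention of having 40 participants in each group". Section 5.0 sets equal allocation and clinic visits at four and eight weeks.

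**The concern.** A blinded reading of photographs and a parent's view of improvement are often recorded as ordered grades, such as worse, same, better. If that is so here, the only categorical test the plan names is a poor match. Pearson chi-square treats grades as unordered labels and gives the same p-value however they are shuffled. With three arms it spends 4, 6 or 8 degrees of freedom on 3, 4 or 5 grades, where an ordered test spends 2.

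These outcomes matter. The picture reading is the only one the plan describes as blinded, and the survey is the only one reported by parents. With 40 per arm there is little sensitivity to spare. Because neither test is assigned, the same grades could be analysed either way, with the choice made after the data are seen.

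**Working it through.** **Inputs from the documents.** Three arms, 40 per arm, 3 × 40 = 120, which agrees with the stated total. There is no planned power to reproduce: alpha, effect size, grade distribution and dropout are not given.

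**Assumptions.** Alpha 0.05; 40 analysed per arm; two arms alike and one shifted under proportional odds; odds ratio (OR) 1.5 to 3. Reference grades: 3 levels (.2, .4, .4); 4 levels (.15, .3, .35, .2); 5 levels (.1, .2, .3, .25, .15); skewed 5 levels (.05, .1, .2, .3, .35).

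**Step 1: the shift.** Divide each cumulative odds by the OR. For 3 levels at OR 3, the cumulative probabilities .2 and .6 have odds 0.25 and 1.5. Divided by 3 these are 0.083 and 0.5, giving cumulative probabilities .077 and .333. The shifted arm is therefore (.077, .256, .667).

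**Step 2: large-sample check at OR 3.** With p_ij the probability of grade j in arm i and p̄_j its mean over arms, the chi-square noncentrality is λ = 40 Σ_i Σ_j (p_ij − p̄_j)² / p̄_j. For Kruskal-Wallis, λ = 40 Σ_i (m_i − 0.5)² / v, where m_i is the arm mean of the pooled mid-rank scores (scaled 0 to 1) and v is their variance.

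| Grades | Chi-square λ, df, power | Kruskal-Wallis λ, df, power |
|---|---|---|
| 3 | 7.98, 4, 60% | 7.90, 2, 71% |
| 4 | 9.16, 6, 60% | 9.01, 2, 77% |
| 5 | 9.49, 8, 56% | 9.32, 2, 79% |

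The signal λ is almost the same for both tests. The loss comes from the extra degrees of freedom, which is why it grows with the number of grades.

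**Step 3: simulation** (100,000 trials per scenario, Monte Carlo standard error under 0.2 points). Cells show chi-square power / tie-corrected Kruskal-Wallis power in percent, with the difference in points in brackets.

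| Grades | OR 1.5 | OR 2 | OR 2.5 | OR 3 |
|---|---|---|---|---|
| 3 | 11.7 / 15.0 (3.3) | 27.3 / 36.0 (8.7) | 45.5 / 57.2 (11.7) | 61.1 / 72.8 (11.7) |
| 4 | 10.6 / 15.8 (5.2) | 25.2 / 39.3 (14.1) | 43.0 / 62.3 (19.3) | 60.0 / 78.8 (18.8) |
| 5 | 9.8 / 16.4 (6.6) | 22.2 / 40.2 (18.0) | 39.0 / 63.8 (24.8) | 55.4 / 80.1 (24.7) |
| 5, skewed | 9.1 / 15.7 (6.6) | 20.5 / 38.1 (17.6) | 35.4 / 60.2 (24.8) | 49.8 / 76.2 (26.4) |

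Three equally likely grades at OR 3 give 64.9 against 75.9, a loss of 11 points, which sets the lower end for OR 2.5 to 3. With no difference between arms, both tests reject in 4.6 to 5.0% of trials.

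**Step 4: where the loss shrinks or reverses.**
- *Two categories:* Kruskal-Wallis equals chi-square times 119/120, so nothing is lost. For 50%, 50% and 75%, both have about 67% power.
- *ANOVA on integer grade scores:* at OR 3, power is 71.4, 78.1 and 79.4% for 3, 4 and 5 grades, within about 1 point of Kruskal-Wallis. On the skewed scale it is 71.5%, about 5 points lower.
- *Movement to both extremes:* with arms (.30, .40, .30), (.30, .40, .30) and (.45, .10, .45), the mean mid-rank is 0.5 in every arm. Kruskal-Wallis therefore sees no signal (power about 6%), while chi-square has about 84%.

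**The case against.** The strongest reply is that the plan never commits to chi-square for these outcomes. ANOVA is named beside it, and ANOVA on grade or total scores keeps the order and nearly all the power. This stands. A reader might infer that Section 10.0 prescribes chi-square for the picture and survey results, but the text ties no test to any outcome.

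Second, nothing in the documents says these outcomes are categorical or ordered. The picture reading could be a numeric score or a yes/no judgement, and the one categorical state the protocol describes, tissue still present after three weeks of treatment (Section 5.0), is binary. This also stands, so the point is conditional on ordered grades.

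Third, a reader might take the upper figures as the loss this trial will suffer. They rest on assumed odds ratios, grade distributions and a consistent shift, a pattern that favours ordered tests. At OR 1.5 the loss is only 3 to 7 points, and with three grades it stays near 12 points or below in the scenarios tabulated.

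Fourth, the ordered test has a real weakness: the both-extremes example costs it almost all its power. That pattern is a special case when the question is which treatment reduces tissue and symptoms more, but it justifies reporting the full table.

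What remains is that the plan names no method designed for ordered categories, leaves the choice between two tests open, and describes no analytic use of a pre-treatment survey answer it will already hold.

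**Conclusion.** The point holds in conditional form. If the picture reading or survey items have three or more ordered grades and are analysed by chi-square, the loss against Kruskal-Wallis with 40 per arm is about 3 to 7 points at OR 1.5, 9 to 18 at OR 2, and 11 to 26 at OR 2.5 to 3, larger with more grades. Only the arm size comes from the documents; alpha, the number and distribution of grades, the one-arm-different pattern and the proportional-odds shift are assumed.

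A further inference to avoid is that a more sensitive test would let the trial conclude the treatments are equal. Section 2.0 aims to show kenalog equal or better but gives no margin, and a difference test of any power does not fill that gap. This is an inexpensive improvement to an under-specified analysis, not a flaw that invalidates the trial.

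**What to change.** In Section 10.0, state the response scale of the picture reading and of each survey item, then add:

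- Chi-square is used for two-category or unordered outcomes.
- Picture grades and survey items with three or more ordered answers are compared across the three arms with a proportional-odds model (or Kruskal-Wallis). Where the same item was asked before treatment, that answer enters the model as a covariate. Odds ratios between arms are reported with 95% confidence intervals.
- The full table of grades by arm is shown beside each test, so that movement to both extremes is visible.

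The cost is a few sentences and no new data, since the pre-treatment survey is already planned. The price is lower sensitivity to effects that are not a consistent shift, which the table addresses only descriptively. Any claim of equality would still need its own margin.
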